## **5.2 Randomization**

At baseline, patients will be randomized according to a randomization scheme (ratio 1:1 for intervention vs control generated by a Statistician at Akershus University Hospital) and administered by a co-worker at Akershus University Hospital who does not take part in the study. The PI, or any other member of the study group, plays no role in the randomization process and will not be given access to the randomization scheme during the recruitment period. There is no blinding procedure (open clinical trial).

## **5.3 Statistical Analysis**

All statistical tests will be performed using a 5% significance level unless otherwise stated. We will calculate delta values for efficacy variables (change from baseline to the final visit) for the intervention and control groups. The main statistical approach will be t-test for independent groups. For the composite end-point of positive SARS CoV2 test, hospitalization or death we will use odds ratio as the outcome measure.

Demographics and efficacy data will be summarized using means and standard deviations for normally distributed continuous variables, medians and interquartile range for non-normally distributed continuous variables and percentages for categorical variables.

Subgroup analysis will be performed according to (high vs low) educational level and modality of renal replacement therapy.

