### 2.2 Objectives

Primary objective:

- Digital health literacy, measured by eHEALS.

Secondary objectives:

- Health literacy, including functional, interactive and critical literacy, measured by HLQ.
- Self-perceived health, measured by EQ-5D-5L.
- Degree of concern for Covid-19, measured by Fear of corona scale

Additional objectives:

- Proportion of patients feeling overwhelmed by the amount of coronavirus information.
- Proportion of patients finding it difficult to get information about the coronavirus in their native tongue.
- Composite end-point of positive SARS CoV2 test, hospitalization and death regardless of cause during the first two years after the intervention.

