For patients randomized to the *intervention group*, the Investigator will take on a more active part and make a new appointment with the patient (a new study visit) within 7 days following the baseline visit, either as a regular meeting, a digital meeting (e.g. zoom) or a telephone meeting. The patient will be asked to seek information available at the LNT website and watch the information videos found at this website, plus seek information available at the Norwegian Health Authority websites, before the new study visit. At the study visit the patient will be asked to give a short resume of take home messages from these websites that he/she find useful in everyday life. They will be asked if they have any questions regarding the information presented at these websites, followed by a teach-back procedure, which aims to ensure that key messages are presented in a way that the patient can understand, correct any misconceptions and show strategies to critically assess digital health information. The patient will be asked to present their strategy to find updated reliable health information available on the Internet. The teach-back method aim to reveal topics where there is a need to further modify and/or repeat information to make it possible to understand for the patient.

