### **5 STATISTICAL CONSIDERATIONS**

#### **5.1 Determination of Sample Size**

There is no previous data from trials to base any power analysis on for this study, thus it is appropriate to base sample size calculation on Tabachnick and Fidells formula  $N \geq (8/f^2) + (m-1)$ , where  $f^2$  is set at 0.05, hence 160 patients need to complete the trial (23). With an expected drop-out rate of 20% the calculated sample size is 192. However, this estimate is solely based on mathematical principles and not patient observations. Thus, should concurrent studies performed on a related topic provide data on which we can base power analysis, we will ask REK for approval to adjust the sample size accordingly. In addition, we aim for inclusion of  $\geq 50$  patients with other native tongue than Norwegian, Swedish, Danish or English, as this is an important subgroup.

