### **6.2 Informed Consent**

The PI and his designates is responsible for giving the patients full and adequate verbal and written information about the nature, purpose and risk/benefit of the study. They will be informed as to the strict confidentiality of their patient data, but that medical records will be reviewed for trial purposes by the PI in order to record data on SARS Cov2 tests and hospitalizations during two years of follow-up. It will be emphasized that the participation is voluntary and that the patient is allowed to withdraw from the study whenever she/he wants. Moreover, it will be emphasized that study participants need not respond to all questions. Participants need not give a reason for why they choose not to respond. Informed consent is mandatory before performing the baseline semi-structured interview in accordance with the national regulatory requirements. The study subjects must be provided with reasonable time to read and understand the Participant Information Form before giving written informed consent to participate in the study. We have included a shortened modified version of the CRF in Norwegian and English attached to The Participant Information Form, hence they will know what kind of questions they will be faced with. At the baseline and end of study visits the questions included in the interview will be handed out to them. Upon request the patient will be provided with a verbal translation of the Participant Information Form in the patient's native tongue (if other than English or any Scandinavian language), as described in section 4.1.2. The PI is responsible for keeping a list of all study subjects including in the study. In the electronic CRF a study participant will be identified by the randomization number only.

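### Section 5.3 fixes an unadjusted t-test on change scores that by default omits the 20% expected to be lost, and it is biased, in either direction, if loss works differently in the two arms

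*Protocol*

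**What the plan says.** The primary objective in section 2.2 is "Digital health literacy, measured by eHEALS". Section 5.3 fixes how this and the other efficacy scales are analysed: "We will calculate delta values for efficacy variables (change from baseline to the final visit) for the intervention and control groups". It continues: "The main statistical approach will be t-test for independent groups", with "All statistical tests will be performed using a 5% significance level unless otherwise stated". No adjustment for baseline is named.

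Section 5.1 sizes the trial on patients who finish. The effect size f² "is set at 0.05, hence 160 patients need to complete the trial", and then "With an expected drop-out rate of 20% the calculated sample size is 192". Section 6.2 adds another source of incomplete data: "it will be emphasized that study participants need not respond to all questions".

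Section 5.2 states that the trial is open with 1:1 allocation. Section 4.1.2 describes a contact that only the intervention arm has. The investigator will "make a new appointment with the patient (a new study visit) within 7 days following the baseline visit", and the patient is asked to go through the websites and videos beforehand. The same section asks participants in both arms to study the material. Section 4.3 intends to keep following and assessing patients who withdraw, unless they refuse contact.

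**The concern.** The protocol chooses a variable that is undefined without a final score, pairs it with a test that uses only defined values, and in the same chapter predicts that one patient in five will be lost. Randomisation protects the comparison of everyone randomised. It does not protect the comparison of those who remain, unless loss is unrelated to change or acts alike in the two arms.

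There is a reason to doubt that it acts alike. At the extra visit, intervention patients summarise what they found, go through teach-back and present their search strategy. That demand bears on the very trait the primary endpoint measures. Patients with low digital literacy or frailty could leave that arm for a reason that controls do not have. A plain t-test on change can neither detect nor correct this. The same analysis serves the HLQ, the Fear of corona scale and the EQ-5D-5L.

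**Working it through.** **The plan's own figures.** Section 5.1: 8/0.05 = 160 (taking m = 1), and 160 × 1.2 = 192, so both stated numbers reproduce. At 20% loss, 192 × 0.8 = 153.6 patients have a change score and 38.4 do not, about 19 per arm. For two equal groups f² = 0.05 corresponds to d = 2√0.05 = 0.447 SD. At that d, power is 0.807 with 80 per arm and 0.791 with 76.8 per arm. Lost precision is therefore minor, and the issue is bias.

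**Bias formula.** Assume no true effect and an SD of change of 1. In one arm let q be the share lost and g the amount by which the mean change of lost patients falls below that of completers. With an all-randomised mean of 0 and a completer mean c, (1 − q)c + q(c − g) = 0, so c = qg. Then:

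- bias = qI·gI − qC·gC (I = intervention, C = control)
- SE = √(1/nI + 1/nC), with n = 96(1 − q)
- type I error = P(|Z + bias/SE| > 1.96). Two-sided 5% is assumed, as section 5.3 does not state sidedness.

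Example: loss 25% vs 15%, g = 0.5 in both arms. Bias = 0.125 − 0.075 = 0.05. SE = √(1/72 + 1/81.6) = 0.162. The ratio is 0.31 and the type I error 6.1%.

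All values of q and g below are assumptions. Overall loss is held at the plan's 20%.

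| Loss I / C | g, I / C (SD) | Bias (SD) | Share of d = 0.447 | Type I error |
|---|---|---|---|---|
| 20% / 20% | 0.5 / 0.5 | 0 | 0% | 5.0% |
| 25% / 15% | 0.5 / 0.5 | 0.05 | 11% | 6.1% |
| 20% / 20% | 0.5 / 0 | 0.10 | 22% | 9.5% |
| 30% / 10% | 0.5 / 0.5 | 0.10 | 22% | 9.4% |
| 25% / 15% | 0.5 / 0 | 0.125 | 28% | 12.1% |
| 30% / 10% | 1.0 / 1.0 | 0.20 | 45% | 23.3% |
| 30% / 10% | 0.8 / 0 | 0.24 | 54% | 31.4% |

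The last two rows are extreme. If lost patients would have changed more than completers (g negative), the sign of the bias reverses.

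**Loss that depends on baseline.** Two simulations used 96 per arm, no effect, and 30% vs 10% loss. Intervention loss was logistic in a baseline variable (slope −1 per SD) and control loss was random.

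- The variable correlates +0.3 to +0.5 with change: the change-score t-test is biased by 0.075 to 0.127 SD in favour of teach-back, with type I error 8.2% to 12.5%. A model containing the variable has bias about 0 and type I error 5.2% to 5.3%.
- The variable is the baseline score itself, with assumed test-retest correlation r = 0.6 or 0.8 and equal variances. Its correlation with change is −√((1 − r)/2) = −0.45 or −0.32. The t-test is now biased against teach-back, by 0.11 or 0.08 SD, with type I error 10.6% or 7.6%. Analysing the final score adjusted for baseline gives bias about 0 and type I error about 5%.

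The clean result for the adjusted models follows from the set-up, since loss depended only on a variable in the model. It shows what adjustment can remove. It does not show that all bias would go.

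**The case against.** The strongest reply is that analysis sets and missing-data methods commonly belong in a statistical analysis plan, which is not at hand. That would dispose of a complaint about silence. It does not dispose of this one, because section 5.3 positively names the variable and the main test. An analysis plan that followed it would inherit the weakness.

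Other parts of the reply stand and limit the point. There are four stronger readings that a reader might infer and that the documents do not support:

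- *The protocol restricts the analysis to completers.* It says no such thing. The 160 in section 5.1 is a sizing figure, and a change score can be compared after imputation. Omission is the default consequence of the stated method. Section 4.3 may also recover final scores from some who withdraw.
- *Only the intervention arm is given work to do.* Section 4.1.2 asks both arms to study the same material. What is one-sided is the extra visit, which may be by telephone or video, and preparation for it.
- *The bias must flatter teach-back.* The endpoint is change, and low baseline scorers may gain more through regression to the mean. Losing them would then count against teach-back, as the second simulation shows.
- *Every skipped question removes a patient.* A skipped item need not void a scale score. Item scoring and the reporting of deaths are details for an analysis plan and form no part of this point.

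Finally, differential loss is plausible but undocumented, and all the magnitudes rest on assumed loss patterns.

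**Conclusion.** The point holds in a limited form. Section 5.3 commits the trial to an unadjusted change-score t-test that by default leaves out about 38 of 192 randomised patients. That comparison is trustworthy only if loss is unrelated to change or works the same way in both arms, and the design gives some reason to doubt this.

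Under moderate asymmetry the bias is about 0.05 to 0.125 SD, or 11% to 28% of the effect the trial is sized on, with type I error about 6% to 12%. It is larger under extreme asymmetry and zero under symmetry. The direction cannot be known in advance. These figures assume 96 per arm, 20% overall loss, no true effect and a two-sided 5% test. The loss rates by arm and the gaps between lost and retained patients are illustrative, since the protocol gives none. The weakness does not invalidate the design, but a better analysis is available from data the trial already collects, so section 5.3 should be changed.

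**What to change.** In section 5.3, make the main analysis a comparison of all randomised patients in their allocated arm, whether or not the teach-back took place. Use the final score as outcome and adjust for the baseline score. Multiply impute missing final scores separately by arm from baseline scores, Clinical Frailty Scale, Charlson index, CKD stage and renal replacement modality (flowchart and section 4.1.2), plus educational level, which section 5.3 already needs for its subgroup analysis.

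Add a delta-adjusted (tipping-point) sensitivity analysis that shifts imputed scores in the intervention arm until the conclusion changes. This covers loss that depends on the unseen outcome, which imputation from baseline cannot correct. Keep the change-score t-test in patients with both scores as a supportive analysis.

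The cost is a few sentences and modest extra programming, with no new data, visits or patients. The downside is reliance on an imputation model, and intervals that carry the uncertainty from missing scores. Baseline adjustment gives something back: with equal variances and test-retest correlation r, the residual variance relative to that of the change score is (1 − r²)/(2(1 − r)) = (1 + r)/2, that is 0.8 at r = 0.6 and 0.9 at r = 0.8.

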#### 4.1.1 Flowchart

	Screening and Baseline visit	Within next 7 days	3 (-4) month Final visit	24 month follow-up
Screening for inclusion in trial	•			
Eligibility assessment and study enrollment	•			
Obtaining written informed consent	•			
Semi-structured interview	•		•	
eHEALS, a measure of digital health literacy	•		•	
HLQ, a measure of functional, interactive and critical literacy	•		•	
Fear of corona scale, anxiety / concern for Covid-19	•		•	
EQ-5D-5L, self-perceived health	•		•	
Question: Difficulty finding information in native tongue	•		•	
Question: Feeling overwhelmed by Covid-19 information	•		•	
Interviewer's assessment of Clinical Frailty Score	•		•	
Randomization	•			
Presentation of websites, including LNT information videos	•			
Study intervention (teach-back method)		•		
Medical record assessment	•			•
Charlson comorbidity index	•			

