#### 4.1.2 Study Visits, Assessments, Data Recording and Investigator Delegation Procedure

Three study visits will be performed as presented in the flowchart. The Investigators will conduct a semi-structured interview and fill in an electronic CRF, which will be dated to ensure correct follow-up time, and to correct for events occurring during the study period that might influence participant responses. Data will be recorded directly into the electronic CRF at the baseline and final visits.

At the baseline visit a semi-structured interview will be performed, followed by a presentation of the LNT website (21). By early December 2020 this website will contain 20 short videos with information tailored for patients with CKD and organ transplant recipients on the topics SARS CoV2, Covid-19, the coronavirus pandemic, the coronavirus infodemic and strategies to critical assess of available digital sources of health information. These videos also contain a short presentation of updates reliable health information sources at the Norwegian Health Authority websites fhi.no, helsenorge.no and imdi.no (1, 6, 7), included where they can find information translated to various languages and where they can find links to other reliable digital health information sources at these websites. The videos are created by the study group and will be filmed and edited at Akershus University Hospital. They will be made originally in Norwegian and English, followed by translation and dubbing to several other languages, similar to previous patient information projects at Akershus University Hospital (22). All study participants will be presented to this source of health information at baseline and asked to study it closely.

For patients randomized to the *control group*, the Investigator will present them with the information videos available at the LNT website (21) and the Norwegian Health Authority websites (1, 6, 7), which would be regarded as within the frame of standard care, although this service is seldom provided at present.

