#### **4.5 Study Amendments**

Should it be necessary for the study protocol to be amended, the amendment will be notified to and sent for approval to local and national regulatory authorities (Personvern Akershus University Hospital and REK). The current Participant Information Form contains information about possible future amendments and need of a second consent before enrollment in future studies.

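### The main analysis is an unadjusted t-test on change scores; adjusting the final eHEALS score for the baseline value already collected would usually be more precise, at almost no cost

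*Protocol*

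**What the plan says.** Section 2.2 gives a single primary objective: "Digital health literacy, measured by eHEALS". The flowchart in section 4.1.1 schedules "eHEALS, a measure of digital health literacy", at the baseline visit and again at the 3(-4) month final visit. Section 4.1.2 confirms the collection: "Data will be recorded directly into the electronic CRF at the baseline and final visits".

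Section 5.3 then sets the analysis: "We will calculate delta values for efficacy variables (change from baseline to the final visit) for the intervention and control groups". The test follows: "The main statistical approach will be t-test for independent groups". No covariate is named there, and no baseline adjustment appears anywhere else in the protocol. The significance level is 5%, with sidedness not stated.

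**The concern.** A t-test on change scores is the same as comparing final scores after subtracting exactly 1 times the baseline score. That is the best multiple only if the slope of final on baseline is 1. The true slope is the correlation times the ratio of final SD to baseline SD. For a questionnaire score measured with error it will often be below 1. The change score then over-corrects for baseline and adds noise to the comparison.

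The same fact can be seen within a single trial. If one arm starts higher by chance, the change-score estimate is shifted in the opposite direction by (1 - slope) times the baseline difference (regression to the mean). ANCOVA removes this shift. The shift is not a second harm on top of the wider interval; it is where the extra variance comes from.

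At stake is the width of the confidence interval for the primary endpoint, and for the other questionnaire scores, to which section 5.3 applies the same approach. Section 5.1 concedes that no earlier trial data support the sample size, so the sponsor cannot count on having power to spare.

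**Working it through.** **Inputs from the protocol.** 160 completers and f² = 0.05 (section 5.1); 1:1 allocation (section 5.2), hence 80 completers per arm; 5% level (section 5.3).

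**Assumptions, because the protocol is silent.** Two-sided testing; correlation ρ between baseline and final eHEALS from 0.3 to 0.9; equal SDs at both visits unless stated otherwise; f² read as a standardized difference for two equal groups, d = 2√0.05 = 0.447.

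**The plan's own figure.** 8/0.05 + (m - 1) = 160 for m = 1 (161 for m = 2). The stated 160 is reproduced.

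**Variance ratio.** Set the baseline SD to 1 and the final SD to k.

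- Variance of change: 1 + k² - 2ρk.
- Residual variance in ANCOVA: k²(1 - ρ²).
- For k = 1 the ratio is (1 - ρ²) / [2(1 - ρ)] = (1 + ρ)/2.

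The interval width scales with the square root of this ratio.

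| ρ | Variance ratio, ANCOVA / change | 95% CI narrower by | Completers for ANCOVA to match 160 (160 × ratio) |
|---|---|---|---|
| 0.3 | 0.65 | 19% | 104 |
| 0.5 | 0.75 | 13% | 120 |
| 0.6 | 0.80 | 11% | 128 |
| 0.7 | 0.85 | 8% | 136 |
| 0.9 | 0.95 | 2.5% | 152 |

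**Unequal SDs, same range of ρ.** With k = 0.8 the ratio runs from 0.50 to 0.64. With k = 1.25 it runs from 0.78 to 1.00. It reaches 1.00 at ρ = 0.8, where the slope is 0.8 × 1.25 = 1 and both variances equal 0.5625. For large samples it never exceeds 1.

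**Power, as an illustration** (noncentral t, 80 per arm; 158 df for the t-test, 157 for ANCOVA). The protocol does not say on which scale the effect is expressed, so both readings are shown.

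(a) d = 0.447 in SDs of the change score. The noncentrality is 0.447 × √40 = 2.83 for the t-test and 2.83/√((1 + ρ)/2) for ANCOVA.

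(b) d = 0.447 in SDs of the raw score. The standardized effect is 0.447/√(2(1 - ρ)) for the t-test and 0.447/√(1 - ρ²) for ANCOVA.

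| ρ | (a) t-test | (a) ANCOVA | (b) t-test | (b) ANCOVA |
|---|---|---|---|---|
| 0.3 | 80.3% | 93.7% | 66.1% | 83.8% |
| 0.5 | 80.3% | 90.1% | 80.3% | 90.1% |
| 0.7 | 80.3% | 86.2% | 95.2% | 97.6% |
| 0.9 | 80.3% | 82.2% | >99.9% | >99.9% |

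**Chance imbalance.** With 80 per arm, the difference in baseline means has an SD of √(2/80) = 0.16 baseline SDs, so its 95% range is about ±0.31. For an imbalance of 0.2 SD, the change-score estimate shifts by (1 - ρ) × 0.2: 0.14 SD at ρ = 0.3, 0.08 at 0.6 and 0.02 at 0.9.

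**Simulation** (6,000 trials per setting, 80 per arm, effect on scale (a)). Power for t-test and ANCOVA was 79.2% and 93.2% at ρ = 0.3, 80.2% and 87.7% at 0.6, and 80.3% and 82.3% at 0.9. Type I error was 4.9% to 5.3% for both methods, and the mean error of both estimates was about zero.

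**The case against.** The strongest reply is that nothing here is wrong. The t-test on change is unbiased under randomization and holds its type I error, and section 5.3 is consistent with the objectives and the flowchart. That is correct and limits the point to efficiency. It does not remove the point, because a better use of the same data is available almost free.

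A second reply is that covariates are commonly left to the statistical analysis plan. That would carry weight if the protocol were silent, but it names both the outcome variable and the test.

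A third reply is that the size of the gain is unknown. This stands. The protocol gives no correlation, SD or eHEALS effect. The gain could be large, could be only 2.5% of the interval width, and disappears if the slope is 1. The power figures rest on a reading of f² that the protocol does not make, and on all 160 completers being available; 192 patients with 20% drop-out leave 192 × 0.8 = 153.6. They illustrate the comparison and do not state this trial's power. The direction does not depend on them.

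A fourth reply is that changing a prespecified primary analysis in an open trial can look data-driven once outcomes are in hand. This is a fair caution about timing.

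Section 6.2 lets participants skip questions, so some baseline scores may be missing. A missing baseline also prevents the change score from being formed, so this does not favour the present plan.

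**Conclusion.** The concern holds. The protocol fixes an unadjusted comparison of change scores where adjustment for the same baseline value would generally be more precise. It is a matter of efficiency on the primary endpoint, worth correcting but not a threat to validity. With equal SDs and ρ between 0.3 and 0.9, both assumed, the variance would be 35% to 5% lower. The benefit is substantial at low correlation, small at high correlation and nil at a slope of 1. In a 1:1 randomized comparison of this size there is no material downside whatever the correlation proves to be. The algebra is certain; the practical size depends on values the protocol does not give.

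**What to change.** In section 5.3, replace the sentence naming the t-test with wording such as:

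> The primary analysis compares eHEALS at the final visit between arms by linear regression (ANCOVA) with treatment arm and baseline eHEALS as covariates; the adjusted mean difference with its 95% confidence interval is the primary result. The HLQ scales, the Fear of corona scale and EQ-5D-5L are analysed with the same model, each with its own baseline value. Delta values are summarised descriptively, and the independent-groups t-test on deltas is a sensitivity analysis.

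The text should also name the EQ-5D-5L score to which the model applies. The change must be settled and dated before any outcome is compared by arm, so that the model cannot appear to have been chosen on the results.

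The statistical cost is one residual degree of freedom (158 to 157), with no new data and no further patients. The administrative cost is an amendment under section 4.5, where "the amendment will be notified to and sent for approval to local and national regulatory authorities".
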